7.0 Data Collection Tools

7.1 Symptom Measurement Patient-reported symptom data will be collected using the: (1) **Brief Fatigue Inventory (BFI)**; (2) **MDASI-HN** module of the M. D. Anderson Symptom Inventory (Appendix F and E) and (3) **Epworth Sleepiness Scale (ESS)** (Appendix G). These and other patient-reported outcome questionnaires will be completed face-to-face in the clinic at the time of enrollment. Subsequent assessments during the study period will be collected either face to face in the clinic, through phone calls by field coordinators or study staff, by Interactive Voice Response (IVR) system, or by regular mail, as outlined in the Assessment Schedule (Appendix X).

Interactive Voice Response (IVR) system combines the use of touch-tone telephones with computers and the Internet to follow patients who have symptoms like pain that need to be monitored closely while away from the hospital. Using the telephone keypad, of a touch-tone telephone, a patient rates his/her pain at its worst in the past 24 hours from 0 (no pain) to 10 (pain as bad as you can imagine). Even when the patient responds using the keypad, these systems are referred to as interactive voice response (IVR) systems. An IVR system should be especially helpful for assessing symptoms such as pain, fatigue, distress, or sleep disturbance that patients may be reluctant to report to their treatment team. The IVRS is programmed to contact patients at their preferred times on specified dates. Once a contact is made, the symptom assessment script runs. Patient responses to the symptom and interference questions are deposited into a web-based database with real-time updates. Brochure describing how to report symptoms through the IVRS will be provided to patients who choose to use it (Appendix HH).

7.2 Measure of Quality of Life The EuroQol (EQ)-5D is a standardized instrument for use as a measure of health outcome (Appendix L). Applicable to a wide range of health conditions and treatments, it provides a simple descriptive profile and a single index value for health status. The EQ-5D was originally designed to complement other instruments but is now increasingly used as a standalone measure. The EQ-5D descriptive system consists of 5 dimensions: mobility, self-care, usual activities, pain/discomfort, and anxiety/depression. Each dimension has 3 levels, reflecting "no health problems" (level 1), "moderate health problems" (level 2), and "extreme health problems" (level 3). A dimension for which there are no problems is said to be at level 1, while a dimension for which there are extreme problems is said to be at level 3. Each unique health state described by the instrument has an associated 5-digit descriptor ranging from 11111 for perfect health to 33333 for the worst possible state. The resulting descriptive system defines 243 health states. In addition, "unconscious" and "immediate death" are included in the EQ-5D valuation process but are not a part of the descriptive system.

7.3 Measure of Global Quality of Life The Global Quality of Life (GQL) is a single item asking patients to rate their quality of life on a 0 to 10 scale over the past week (Appendix M).

7.4 Measure of Patient Satisfaction with Study Medication The Study Medication Satisfaction Scale is a short questionnaire that asks patients about several areas of satisfaction (Appendix N). The scale includes questions about ease or difficulty of taking the medication in general and in its current form, the convenience of taking the study medication as instructed, and patient confidence that the study medication is of benefit.

7.5 Work Productivity and Activity Impairment Questionnaire (WPAI) (Appendix H)

7.6 Head and Neck Treatment Summary Form (Appendix O)

7.7 Patient Contact Form (Appendix P)

7.8 Demographic Form The Demographic Form includes patient birth date, gender, marital status, race, ethnicity, education, and employment status (Appendix Q). The Demographic Form will be completed at baseline.

7.9 Charlson Comorbidity Index The Charlson Comorbidity Index yields a comorbidity score, to control for serious concurrent chronic disease conditions (Charlson et al., 1994) (Appendix R).

7.10 On-Study Form The On-Study Form contains data about disease, previous treatment, whether a patient is on concurrent protocols (Appendix S). This form will be completed at baseline.

7.11 Clinical Monitoring Form The Clinical Monitoring Form contains clinical data, including Body Mass Index (BMI), blood pressure, pulse rate, performance status, symptom treatment, and CTC toxicity scores (Appendix T).

7.12 Medication Form The Medication Form contains data about types of medications patients have been prescribed. Medication types include pain medications, antiemetics, and psychotropics among others. There is also a general section for other types of medications patients may be taking. (See Appendix U).

7.13 Patient Disposition Form Patient's final disposition will be collected on the Patient Disposition Form. Patients who are satisfied with the study medication and express interest in continuing will be able to discuss continuing armodafinil as part of physician-patient decision based on a risk-benefit scenario, with further clinical monitoring to continue under the care of the patient's treating physician. Subjects with persistent moderate to severe levels of fatigue will be offered further evaluation and referral to the MD Anderson Fatigue Clinic (Appendix V).

7.14 Study Medication Accountability Form This form contains study medication data, including the number of tablets dispensed to the patient at the last visit to the outpatient pharmacy, how many tablets were returned from the last visit, and the number of days the tablets were taken (Appendix K).

7.15 Laboratory Data Form No study-specific labs are planned; however, any blood-analysis values obtained for clinical reasons will be captured on the Laboratory Data Form, including C-reactive protein (CRP), serum chemistry (albumin, calcium, phosphorous, glucose, BUN, creatinine, total bilirubin, and total protein), electrolytes (sodium, potassium, chloride, carbon dioxide, magnesium), and complete blood count (CBC). These values will be recorded if they are available in the patient medical record from a blood draw performed for clinical purposes within previous 2 weeks. Note: Liver function tests are required at baseline. If they were not performed within the past 2 weeks prior to starting treatment with the symptom drug/placebo, they will be drawn for eligibility purposes. (Appendix W).

7.16 Treatment Summary Form The Treatment Summary Form contains data about previous radiation therapy and cancer treatment (Appendix O).

7.17 Final Study Status Form The Final Study Status Form contains data about patient disposition at the end of the study (i.e., completed study, withdrew, vital status, tumor status) (Appendix Y).

8.0 Patient Eligibility

8.1 Inclusion Criteria

8.11 Patients who were treated with either definitive or postoperative radiation or chemoradiation therapy for HNC with moderate to severe levels of patient reported fatigue, at 6 or more weeks after completing all planned cancer therapy.

Patients who rated their fatigue level at 5 or greater on a 0 to 10 scale during any follow-up clinic visits at MD Anderson.

8.12 Male and female patients \geq 18 years old.

8.13 Patients who speak English (due to the novel research and its complexity, we are only accruing English-speaking patients to the protocol).

8.14 Patients must agree to discontinue any current herbal supplement use, and refrain from taking any herbal supplement while on protocol.

8.15 Patients must be willing and able to review and understand informed consent documents and to provide written consent.

8.16 Women of childbearing potential (women who are not postmenopausal for at least 1 year and are not surgically sterile) must have a negative urine pregnancy test.

8.17 Sexually active males and females must agree to use effective birth control or to be abstinent for the duration of the study period.

8.18 Women currently taking birth control pills or planning to start birth control pills must agree to an additional method of birth control (either abstinence or a barrier method) while on the study medication and for 1 additional month after study completion.

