2.0 Rationale

Fatigue is one of the most severe symptoms reported by patients at any time point assessed in our M. D. Anderson Symptom Inventory - Head and Neck Module studies (Rosenthal et al, ASCO 2010, Rosenthal et al, ASTRO 2010). Further, fatigue severity peaks for approximately one-fourth of patients after treatment completion, and approximately one-third of patients report moderate to severe fatigue at 8 weeks after completion of radiation therapy or chemoradiation (Rosenthal, ASTRO 2010). This is an important time for fatigue-symptom intervention, because many patients are expecting to return to work or to their usual level of functioning around this time frame.

The agent to be tested in this trial is **armodafinil**. Using a blinded, randomized placebo-controlled trial, we will evaluate armodafinil's ability to reduce patient-reported fatigue in patients with persistent moderate to severe levels of fatigue after completion of radiation therapy and all planned cancer therapy. The target of action for the proposed intervention is armodafinil's alertness-promoting property, which could impact patient-reported fatigue, other associated symptoms, and symptom interference with daily activities.

The significance of this research is that it (1) evaluates a commercially available, low-toxicity symptom therapy, (2) evaluates a therapy that could reduce multiple commonly reported symptoms in patients with head and neck cancer by targeting fatigue (one of the most severe symptoms reported by this patient group), and (3) seeks to establish a simple medical symptom-intervention therapy for head and neck cancer, a disease site for which the patient-reported symptom burden is high and few proven medical symptom intervention strategies exist.

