3.0 Background

Cancer was diagnosed in more than 1.4 million people in the United States in 2007 alone — 34,360 with head and neck cancer (HNC) (Jemal et al., 2007). Many of these patients receive aggressive therapy and experience multiple symptoms that cause them significant distress and impair function and rehabilitation. Whereas symptoms are often the result of disease, it is increasingly recognized that pain, fatigue, sleep disturbance, cognitive dysfunction, and affective symptoms can also be caused by cancer treatment. Treatment-related symptoms can directly affect survival if they become so severe that the patient abandons potentially curative therapies (Borden & Parkinson, 1998; Jeremic et al., 2003). Moreover, treatment-related symptoms may persist for weeks, months, or years and may worsen, even if the cancer improves.

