9.0 Patient Enrollment and Registration

Patient Enrollment

Patients will be screened for eligibility and recruited for enrollment in the outpatient Head and Neck Cancer Clinic in the Department of Radiation Oncology at MD Anderson, 6 or more weeks after completing planned cancer therapy (this time line will generally coincide with the first follow up appointment for most patients with HNC treated with radiation therapy). By this time, most patients should have had significant improvement in their radiation therapy-related mucositis, dermatitis, and pain. Recruitment brochures will be available to give to the patients in the clinic (Appendices ZZ and ZZZ).

Patients with major depressive disorder or severe depression (a score of 13 or greater on the BDI Fast Screen (BDI-FS) will be excluded. If this is the case, we will notify their treating physician for appropriate management or referral. The first disease/treatment response assessment is made around this time period as well.

Women of child-bearing potential who want to participate will be told that we will perform a mandatory pregnancy screening test through a urine sample at baseline. Study staff will provide the pregnancy kits to these women and make sure the results are known and recorded in the follow-up notes in Clinic Station before study drug prescription are filled by the Investigational Pharmacy. If the pregnancy test is positive the patient will be excluded from the study.

Research staff will maintain a log of all patients screened, and the reasons that patients do not enter the study will be documented.

Eligible patients who agree to enroll in the study will provide written informed consent/authorization.

At enrollment, patients will be informed that they will receive a \$40 stipend for participating in the pilot study. The stipend will be distributed in \$20 increments twice during the study, at enrollment and at study completion.

Enrolled patients will be registered into the Clinical Oncology Research System (CORe), the MD Anderson institutional patient data management system.

Patient Randomization and Assignment to Treatment Arm

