13.2 Analysis Plan

We will test armodafinil in its ability to reduce values of patient- reported fatigue scores. Our emphasis is to test the efficacy of armodafinil as a potential agent in reducing patient-reported symptoms in patients with HNC after planned cancer therapy. The proposed phase II clinical trial for screening this potentially effective symptom-intervention agent will provide moderate power in detecting modest intervention effect. If the treatment has a more pronounced effect, it will be detected with higher power.

This study will allow us to obtain estimates of treatment effect and the variability of these estimates. Estimates of treatment effect will be obtained using standard linear regression techniques in which AUC values ($hn(i)$) are regressed on indicator variables that represent treatment received. Estimates of treatment effect and between-subject variability will then be used to design a more comprehensive study in future clinical trials.

In addition to the formal evaluation of treatment effects on the primary outcome, we will also examine the prognostic effects of disease stage, type of cancer treatment, ECOG status, age and gender in predicting the outcome variable. We will compare the percentages of patients who were satisfied with the study drug against those who were taking the placebo. We will include an indicator variable in our model to determine whether patients who had a full dose of armodafinil differ from those who had a run-in period. Standard exploratory data analysis techniques and descriptive statistics will be used.

Assuming that patients accrue at the rate of 4 per month, we anticipate that this pilot study will require approximately 14 months to complete.

Intent to treat

We will need at least 2 weeks of BFI data for the patient to calculate AUC. Any patient who drops out prior to this will be replaced.

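### Time since completing therapy is open-ended at entry but absent from the primary AUC model; prespecifying it as a covariate would protect precision at almost no cost

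*Combined protocol and SAP*

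**What the plan says.** **Entry.** Criterion 8.11 recruits patients with moderate to severe fatigue "at 6 or more weeks after completing all planned cancer therapy". It also refers to "Patients who rated their fatigue level at 5 or greater on a 0 to 10 scale during any follow-up clinic visits at MD Anderson", so a qualifying rating is not tied to the first visit. No exclusion in 8.2 caps the time since therapy. Section 9.0 repeats the 6-week minimum and adds that "this time line will generally coincide with the first follow up appointment for most patients with HNC treated with radiation therapy". That is an expectation about recruitment, not a criterion.

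**Why time could matter.** Section 2.0 describes fatigue relative to the end of treatment: "fatigue severity peaks for approximately one-fourth of patients after treatment completion". It then gives a prevalence at a fixed later time, also counted from the end of treatment: "approximately one-third of patients report moderate to severe fatigue at 8 weeks after completion of radiation therapy or chemoradiation". Section 3.0 says that "treatment-related symptoms may persist for weeks, months, or years and may worsen, even if the cancer improves".

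**Randomisation.** Section 9.0 describes one list for all 40 patients, prepared in advance and held by the Investigational Pharmacy. It names no stratification factor.

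**Analysis.** Section 13.2 regresses the AUC on treatment indicators. Separately, it will examine "prognostic effects of disease stage, type of cancer treatment, ECOG status, age and gender in predicting the outcome variable". Time since therapy appears in neither place.

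**Data.** Section 7.16 says the Treatment Summary Form records previous radiation and cancer treatment.

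**The concern.** The outcome is fatigue accumulated over several weeks. If its course depends on how long ago treatment ended, a patient at week 6 and one who is much further out may have different expected AUCs whatever drug they receive. With 20 per arm, the groups can differ by chance in their share of recent finishers, and an unadjusted model leaves that difference in the estimate and its spread in the residual variance. This matters because 13.1 and 13.2 say the trial's main product is an effect size and a variability estimate for a later trial, and because the design accepts only 70% power. A covariate chosen after unblinding would be post hoc; one named beforehand would not.

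**Working it through.** **1. The plan's own figure.** Inputs from 13.1: 20 per arm, effect 0.70 SD, one-sided 5%. The noncentral t with 38 df and noncentrality 0.70 × √(20/2) = 2.21 gives power 70.2% (71.5% by the normal approximation). The stated 70% reproduces.

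**2. Scale.** 13.1 equates 0.70 SD with about 1.7 points, so the implied SD is 1.7/0.70 = 2.43. The unadjusted SE of the arm difference is 2.43 × √(2/20) = 0.77 points.

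**3. Chance imbalance.** Assume 20 of the 40 patients are early and 20 late; the documents give no such figure. Under 20:20 allocation, the number of early patients in one arm is hypergeometric (40, 20, 20).
- 12:8 or worse, in either direction: probability 34%.
- 13:7 or worse: probability 11%.

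If 30 are early and 10 late, an arm difference of at least 4 late patients has probability 27%.

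**4. Effect of a 12:8 split.** The shares differ by 12/20 − 8/20 = 0.20. Assume an early/late gap in mean fatigue of 1 to 2 points; the documents give no value.
- Shift = 0.20 × 1 to 0.20 × 2 = 0.2 to 0.4 points.
- Against the SE: 0.2/0.77 to 0.4/0.77 = 0.26 to 0.52.
- Against the 1.7-point target: 12% to 24%.

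**5. Precision gained, on the same assumptions.** For a two-level factor with early share p and gap g, R² = p(1 − p)g²/2.43². The SE ratio after adjustment is √(1 − R²) × √(38/37). Power uses effect 0.70/√(1 − R²) and 37 df.

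| Early share | Gap (points) | R² | SE reduction | Power |
|---|---|---|---|---|
| 50% | 1 | 4.2% | 0.8% | 71.8% |
| 50% | 2 | 17.0% | 7.6% | 77.0% |
| 75% | 1 | 3.2% | 0.3% | 71.3% |
| 75% | 2 | 12.7% | 5.3% | 75.2% |

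**6. Cost if time is not prognostic.** With R² = 0 and 37 df, power is 70.1% against 70.2% unadjusted (70.12% v 70.16%), a loss of about 0.04 percentage points.

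Steps 3 to 5 use an early/late split for transparency. A continuous (log) time covariate could explain more or less than these R² values.

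**The case against.** Four arguments count against making much of this.

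*The mix may be small.* A reader might infer that the trial will combine recovering patients with survivors years out from treatment. The documents permit that but do not show it: Section 9.0 expects most patients to enter near the first follow-up, and Section 2.0 frames the intervention around 8 weeks. This stands, and is why the 75% rows are shown.

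*Spontaneous recovery is inferred.* Section 2.0 gives no rate of decline after week 6. The improvement by that time mentioned in 9.0 concerns mucositis, dermatitis and pain. Section 3.0 allows symptoms to persist or worsen, and 8.21 excludes anyone whose current worst fatigue is 4 or less. This also stands: the documents do not establish that time since therapy is prognostic among eligible patients, and the 1 to 2 point gap is purely an assumption.

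*There is no bias.* A reader might conclude that natural recovery would be mistaken for drug effect. Randomisation prevents that in expectation, and the unadjusted SE already allows for chance imbalance. The correct description is lost precision, plus a conditional shift if an imbalance happens to occur.

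*The variance is not wrong.* A reader might say that the SD carried forward is inflated. If the next trial keeps the same eligibility and an unadjusted analysis, that SD is the right planning input. It misleads only if either changes.

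None of this explains leaving the variable out. The plan's own rationale is organised around time since treatment, five other prognostic factors are listed, and the covariate costs almost nothing even if it proves uninformative.

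**Conclusion.** The omission is real and worth correcting, as a modest gain in efficiency and clarity. It is not a threat to validity. Entry has no upper time limit, and time since therapy is absent from both the primary model and the listed prognostic factors. Under an assumed half-early population and a 1 to 2 point gap, adjustment reduces the SE by about 1% to 8% and adds about 2 to 7 percentage points of power. With 75% early, the SE reduction is about 0.3% to 5%. The early share and the gap are assumptions; the SD of 2.43 follows from 13.1. If the gap is zero there is no gain and practically no loss. The documents do not support a claim that the planned comparison is biased, or that the entry window is wrong.

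**What to change.** Amend 13.2 before unblinding:

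- Include weeks from completion of all planned cancer therapy to randomisation, on a log scale, as a prespecified covariate in the primary AUC regression.
- Add it to the prognostic factors to be examined.
- Report its distribution by arm in the baseline table, so that the next trial knows which population the estimates describe.

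The completion date is already needed to check 8.11. Confirm that the Treatment Summary Form records it, since 7.16 does not mention dates and the form itself was not available for this review.

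The cost is SAP wording and one degree of freedom (38 to 37). Sample size and eligibility stay as they are. Stratified randomisation is not recommended: it would change the single-list procedure held by the pharmacy, and the covariate adjusts for chance imbalance in this factor without that change.

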4.12 Cautions and Warnings

4.121 Avoid in patients with a history of clinically significant cutaneous drug reaction, or a history of clinically significant hypersensitivity reaction, including multiple allergies or drug reactions

4.122 Caution in patients with a history of angina or cardiac ischemia, a recent history of myocardial infarction or left ventricular hypertrophy, or in patients with mitral valve prolapse

4.123 Induces CYP3A, so avoid midazolam and drugs that are substrates for CYP3A4/5, such as cyclosporine, ethinyl estradiol, triazolam, as dose modification would be needed

4.124 Avoid CYP3A4/5 inducers: carbamazepine, Phenobarbital, rifampin; or inhibitors: ketoconazole, erythromycin

4.125 Moderately inhibits CYP2C19, so avoid omeprazole and drugs that are substrates for CYP2C19, such as phenytoin, diazepam, propantheline, chlomipramine and other tricyclic antidepressants

4.126 Avoid other use in combination with other CNS stimulants, such as methylphenidate, dextroamphetamine, and modafinil

4.127 Caution in combination with MAO inhibitors

4.128 Increased monitoring needed for patients on Coumadin/warfarin

4.129 Clearance may be reduced in the elderly; safety not established for patients over 65

- 4.130 Avoid in patients with history of CNS stimulant abuse, such as methylphenidate, dextroamphetamine, and modafinil
- 4.131 Patients should be cautioned about operating an automobile or other hazardous machinery until they are reasonably certain that armodafinil will not affect their ability to engage in such activities
- 4.132 Steroidal contraceptive effectiveness may be reduced while on armodafinil and for the following month after discontinuing armodafinil – alternative birth control methods recommended during this period

- 4.133 Patients should be advised to avoid alcohol

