4.4 Armodafinil (or Modafinil) Drug Interactions

Induces CYP3A, so avoid midazolam and drugs that are substrates for CYP3A4/5, such as cyclosporine, ethinyl estradiol, and triazolam, as dose modification would be needed

Avoid CYP3A4/5 inducers: carbamazepine, Phenobarbital, rifampin, aminoglutethimide, naftilin, nevirapine, phenytoin; or inhibitors: azole antifungals, clarithromycin, diclofenac, doxycycline, erythromycin, imatinib, isoniazid, nefazodone, nicardipine, propofol, protease inhibitors, quinidine, telithromycin, and verapamil

Moderately inhibits CYP2C19, so avoid omeprazole and drugs that are substrates for CYP2C19, such as phenytoin, diazepam, propanolol, chlomipramine (or other tricyclic antidepressants), citalopram, methsuximide, and sertraline

Oral contraceptives: Serum concentrations may be reduced (due to metabolism enzyme induction); contraceptive failure may result; alternative contraceptive measures are recommended during therapy and for 1 month after armodafinil is discontinued

Warfarin: Serum concentrations/effect may be increased by modafinil; would require increased PT/INR monitoring

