8.27 Patients with a Karnofsky performance status <70

8.28 Patients less than 18 years old

8.29 Patients who are enrolled and receiving active treatment in other symptom intervention trials or who are in the treatment phase of another clinical trial

8.210 Patients with pre-existing psychosis or bipolar disorder

8.211 Patients with pre-existing renal impairment, as evidenced by serum creatinine $>$ ULN on the most recent blood work, done at least within the previous 2 weeks.

8.212 Patients with pre-existing cirrhosis or hepatic impairment or with abnormal liver function test as evidenced by total bilirubin $>1.5 \times$ ULN or 2 times the upper limit of normal of alkaline phosphatase (ALP), alanine aminotransferase (ALT) or aspartate aminotransferase (AST) on the most recent blood work, done at least within the previous 2 weeks.

8.213 Patients with pre-existing Tourette's syndrome

8.214 Patients who have used monoamine oxidase (MAO inhibitors) within the past 14 days

8.215 Patients undergoing abrupt discontinuation of ethanol or sedatives (including benzodiazepines)

8.216 Patients currently taking, or having taken within the previous 1 month, armodafinil, modafinil, amphetamine, or methylphenidate

8.217 Patients on anticoagulants (i.e. warfarin, coumadin, or heparin) or clopidogrel

8.218 Patients with a history of clinically significant cutaneous drug reaction, or a history of clinically significant hypersensitivity reaction, including multiple allergies or drug reactions

8.219 Patients with a history of angina or cardiac ischemia, a recent history of myocardial infarction (within the past 1 year) or left ventricular hypertrophy, or patients with mitral valve prolapse

8.220 Patients with uncontrolled hypertension or tachycardia, as determined by treating physician

8.221 Patients who are pregnant, breastfeeding, or planning to become pregnant during the study period and for 1 month after stopping the study drug.

8.222 Female patients who are currently on birth control pills as primary means of contraception, but are not willing to seek an additional effective method of contraception (such as barrier method) during the study period and for 1 month after stopping the study drug.

8.223 Patients with a history of CNS stimulant abuse, such as methylphenidate, dextroamphetamine, or modafinil.

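### A second contraceptive method is an entry condition only for pill users, although 4.132 warns about steroidal contraceptives without limiting the route

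*Combined protocol and SAP*

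**What the plan says.** **The hazard.** Protocol 4.132 warns: "Steroidal contraceptive effectiveness may be reduced while on armodafinil and for the following month after discontinuing armodafinil". It names no route and adds: "alternative birth control methods recommended during this period". Section 4.4, on drug interactions, speaks of oral contraceptives only: "contraceptive failure may result; alternative contraceptive measures are recommended during therapy and for 1 month after armodafinil is discontinued".

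**The entry rules on a second method.** There are two, and both are about pills.
- 8.18 (inclusion): "Women currently taking birth control pills or planning to start birth control pills must agree to an additional method of birth control". The cover is to last "while on the study medication and for 1 additional month after study completion".
- 8.222 (exclusion) applies to "Female patients who are currently on birth control pills as primary means of contraception" who will not add a further effective method during the study period and for 1 month after stopping the drug.

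**Neighbouring rules.**
- 8.17: "Sexually active males and females must agree to use effective birth control or to be abstinent for the duration of the study period".
- 8.221 excludes women who are pregnant, breastfeeding, or "planning to become pregnant during the study period and for 1 month after stopping the study drug".
- 8.226 excludes anyone currently taking ethinyl estradiol, in whatever product.
- 4.115 lists pregnancy as an absolute contraindication, and 12.15 makes it a reason for removal from the study.

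**The concern.** The protocol identifies a hazard for a class of contraceptives and then makes protection a condition of entry for only part of that class. A pill user who declines back-up cannot enrol. A woman on a different steroidal method, to whom the same caution in 4.132 applies, faces a recommendation only. At stake is an unintended pregnancy on a drug for which the protocol treats pregnancy as a contraindication.

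The second, smaller matter is the point from which the extra month is counted. Four clauses (4.132, 4.4, 8.221, 8.222) count from stopping the drug; 8.18 alone counts from *study completion*. Where open-label armodafinil is taken, these dates can differ in a way that matters.

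**Working it through.** The plan gives no figure on this point, so there is none to reproduce. The check has two parts: a comparison of clauses, and a day count.

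**Who is covered by a mandatory second method**
- Current user of a product containing ethinyl estradiol: excluded outright by 8.226.
- Other current pill user: covered by 8.18 and 8.222.
- Woman planning to start pills: covered by 8.18 only.
- Current user of a non-pill steroidal method without ethinyl estradiol: named in neither 8.18 nor 8.222 and not excluded by 8.226. Back-up is recommended by 4.132. 8.17 applies, but is silent on whether a steroidal method alone counts as effective on this drug.

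The last group is the gap in scope.

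**Inputs for the day count**
- Day 1 is the first dose, and the study period is counted from it (assumption).
- Blinded dosing lasts 4 weeks, so the last blinded dose is on day 28 (sections 5.0 and 6.0).
- The study period is 8 weeks, or 12 with the open-label option (section 5.0).
- Open-label drug lasts 4 weeks and starts 0-5 days after Part I ends (sections 5.0 and 6.0).
- One month is 30 days (assumption; range 28-31).

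**Risk window under 4.132 = last dose + 30**
- No open-label drug: 28 + 30 = day 58.
- Open-label drug: last dose 28 + 28 = day 56 to 28 + 5 + 28 = day 61; window ends 56 + 30 = day 86 to 61 + 30 = day 91.

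**Cover under 8.17 (study period)**
- No open-label drug: to day 56, so 56 of 58 days; tail 58 - 56 = 2.
- Open-label drug: to day 84-89, so 84 of 86 to 89 of 91 days; tail 2.
- The tail equals the month length minus 28, so it is 0-3 days for a month of 28-31 days. It carries little weight.

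**Cover under 8.222 (current pill users):** to last dose + 30, so the gap is 0 with or without open-label drug.

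**Cover under 8.18 for a woman planning to start pills**
1. *Study completion* is the end of follow-up, with continuous cover. Cover ends 56 + 30 = day 86 against 58 needed, or 84 + 30 = 114 to 89 + 30 = 119 against 86-91 needed. The gap is 0, and cover runs 28 days longer than 4.132 asks.
2. *Study completion* is the end of follow-up, read literally as two separate stretches: time on drug, then the month after completion. Without open-label drug, days 29-56 fall between them, which is 56 - 28 = 28 of the 30 days of the risk month.
3. *Study completion* is the end of week 4. Cover ends 28 + 30 = day 58.
   - No open-label drug: gap 58 - 58 = 0.
   - Open-label drug counted as study medication: cover ends day 58 (last dose day 56) to day 61 (last dose day 61); gap 86 - 58 = 28 to 91 - 61 = 30 days.
   - Open-label drug not counted: gap 86 - 58 = 28 to 91 - 58 = 33 days.

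The week-4 reading has a textual basis: section 6.0 uses the term in the paragraph on the medication review at the end of week 4. Section 7.17, by contrast, lists completing the study as a status recorded at the end of the study.

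**The case against.** The case against is substantial.

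- **8.17 may already do the work.** It binds every sexually active patient for the study period. Given 4.132, a steroidal method without back-up is doubtful as effective contraception on this drug. That is a fair reading, but the text does not state it, and 8.18 and 8.222 spell out the second-method requirement for pills alone.
- **Other safeguards exist.** Section 5.0 makes interaction screening a staff responsibility, with review of medications before treatment and medication sheets for patients and physicians. Women of childbearing potential need a negative pregnancy test (8.16, section 9.0). These lower the risk. None of them makes back-up a condition of entry.
- **Pills-only wording matches 4.4.** It does, and that may explain it. 4.132 is still the wider statement, and the documents give no route-specific data for setting it aside.
- **Unseen material.** The consent pages and Appendices EE and EEE are not in the supplied text and may contain contraception advice. That cannot be checked and is not held against the plan.

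A reader might infer that a recommendation in 4.132 contradicts a requirement in 8.18. It does not: an eligibility rule may be stricter than a drug caution. Only the difference in scope matters. A reader might also infer that 8.18 has no defined end. The documents do not support that: it ends 1 month after study completion, most naturally week 8 or week 12 under section 5.0. The fault is an anchor that differs from the other clauses.

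**Conclusion.** The point holds as a minor patient-safety matter.

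**Scope.** For women on a non-pill steroidal method without ethinyl estradiol, back-up is recommended but not required over days 1-58, or days 1-86 to 1-91 with open-label drug. 8.17 and 8.226 narrow this gap without closing it. It would be too strong to say that these women are unprotected, because 8.17 obliges them to use effective contraception or abstain for nearly the whole window.

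**Anchor (secondary).** Current pill users have no gap, because 8.222 covers them. For women planning to start pills, the gap is 0 on the most natural reading, 28 days on the literal two-stretch reading without open-label drug, and 28-33 days if completion means week 4 and open-label drug is taken. Even on those two readings, what lapses is the mandated second method; 8.17 still applies to the end of the study period.

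The day counts rest on a 30-day month and on counting the study period from first dose. The documents give no sex or age mix, so the number of the 40 patients affected cannot be computed; it is probably small, but that is a judgement. Randomization, power and analysis are unaffected.

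**What to change.** In 8.18 and 8.222, replace the reference to birth control pills with any steroidal contraceptive, current or planned, not already excluded by 8.226. In both, require an added non-steroidal method or abstinence from the first dose until 1 month after the last dose of study drug, including open-label armodafinil. This removes the study-completion anchor from 8.18, and the 8.226 carve-out keeps current ethinyl estradiol users from falling under both an outright exclusion and a back-up rule. 8.17, 8.221 and 8.226 can stay as they are.

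The cost is a wording amendment to two criteria, and to the consent form only if it repeats the pills-only rule. A few more women would have to accept a second method, and one who declines could not enrol. No visit or procedure is added.
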